### The following methods will be utilized for completion of visits 1-2:

- Medical History and Physical Exam
- Exercise on stationary bicycle or arm ergometry
- Right heart catheterization
- Arterial line insertion
- Assessment of oxygen consumption (VO2) and carbon dioxide production (VCO2) via metabolic cart
- Assessment of vital signs: heart rate, blood pressure, SpO2, end-tidal carbon dioxide (ETCO2)
- Lactate measurement
- Echocardiography
- 6-minute hall walk
- 10 meter gait speed
- KCCQ and MLHFQ (for LVAD cohort only)
- CRT-D device interrogation (for subjects that have an LVAD and a CRT-D device)

#### Procedures that will occur in the catheterization lab or the inpatient CTRC for visits 1-2:

- Right heart catheterization: insertion of a Millar catheter under fluoroscopic guidance
- Arterial line insertion

[figure not shown]
Protocol Template CF-146, Effective 7/10/11

# Procedures that may occur in *either* the catheterization lab or the inpatient unit of the CCTSI (12th floor of the inpatient hospital):

- LVAD pump speed adjustments: pump speed adjustments will be completed after the Millar catheter and arterial line are inserted and will be completed before patients exercise on the stationary ergometer. The location of testing (catheterization laboratory or CCTSI) will be determined based on schedule availability. If testing is completed in the CCTSI, patients will be transported from the catheterization laboratory by the study PI ([name]), a CCTSI nurse, a cath lab staff member and with telemetry monitoring (same as already being done for IRB study #16-1635).
- Exercise testing: following placement of the Millar catheter and arterial line, exercise testing will either be completed in the catheterization laboratory, or the patient may be transported to the inpatient CTRC unit to complete testing. Following completion of the study, the Millar catheter will be removed under fluoroscopic guidance: if testing is completed in the cath lab, the catheter will be removed there, once testing is completed. If testing is completed in the CTRC, the patient will be brought back to the catheterization laboratory for removal of the catheter.
- Echocardiography
- 6-minute hall walk
- 10 meter gait speed
- KCCQ and MLHFQ
- CRT-D device interrogation (for subjects that have an LVAD and a CRT-D device)

**Team members that will be present at all times during the study**: regardless of the location of the testing (CCTSI v. cardiac catheterization laboratory), the following team members will be present for testing:

- [name] (study PI)
- Study coordinator
- Cath lab staff member
- RN from the CCTSI

**Protocol**: The standard CRT-D pacing mode is CS-lead OFF, so these patients will begin the substudy with their pacemakers in the CS-lead OFF mode. Following enrollment, patients will undergo a sixminute hall-walk as part of the research substudy. Cardiac output will be assessed noninvasively using the Innocor inert rebreathing technique. Thereafter, a transthoracic echo (TTE) will be completed as *part of standard-of-care* (these patients undergo routine echos during clinic appointments). The abovelisted parameters will be recorded. Following completion of the echo, LVAD parameters will be recorded and then the pacemaker will be adjusted to the CS-lead ON setting. Then, patients will complete their routine clinic visit, which typically lasts ~60 minutes. Once completed, the patient will repeat the six-minute hall-walk, as well as cardiac output by inert rebreathing technique, and the same echo images will be repeated. LVAD parameters will be recorded. Once completed, the pacemaker will be returned to original settings, with CS-lead OFF. The procedure will be completed and the patient discharged from clinic.

Compensation: patients will not be provided any further compensation for this substudy. Data Analysis: all outcomes of interest will be compared by paired t-test to determine differences between CS-lead ON v. OFF. LI statistical analyses will be paerformed using a computer-based analysis system (SAS V9.4, Cary NC, USA). A P value of <0.05 will be considered statistically significant.

TTE with Strain Imaging	Innocor Cardiac output	6 minute walk test	Clinic Visit	TTE with Strain Imaging	Innocor Cardiac output	6 minute walk test	
	RV pacing				CRT pacing		

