#### H. Summarize Knowledge to be Gained:

This proposal will be the first to provide a comprehensive assessment of the impact CRT-D pacing strategies on cardiac function for heart failure patients with CF-LVADs. Currently, there is a lack of knowledge about best-practices for management of CRT-D in patients with CF-LVADs. In the absence of data, practitioners frequently deactivate the CS-lead in an effort to conserve CRT-D battery life and also to allow the interventricular septum to contribute to RV contractility. However, my preliminary data suggest that this strategy is not ideal, and that cardiac function (specifically, Qc) improves with the CS-lead activated.

This proposal will be the first to provide a detailed analysis (using high-fidelity Millar catheters) of CF-LVAD therapy on RV performance at rest and with activity/exercise. It is likely that a CF-LVAD compromises RV function by "pulling" the interventricular septum away from the RV (the septum is "pulled" away from the RV by the suction effect created from the LVAD), which increases RV diameter and limits the ability of the septum to contribute to RV contractility.

This study will define short-term benefits as it pertains to functional capacity (as determined by six-minute hallwalk), as well as hemodynamic parameters (as measured by cardiac output) that result from enabling the CS-lead. Further, acute improvements in cardiovascular performance (determined noninvasively by echocardiogram) will be characterized as well.

Findings from these studies will inform clinicians on best-practices regarding CRT-D programming to optimize cardiac function and exercise capacity, will characterize how CF-LVAD technology influences RV function and also define the extent to which RV function/dysfunction limits exercise capacity in these patients.

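### The substudy's text and schedule table give different test orders, and neither says whether cardiac output and echo are taken at rest

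*Combined protocol and SAP*

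**What the plan says.** All of this is in the protocol section on the short-term sub-study.

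- **Text, CS-OFF block.** The walk is the first test named: "Following enrollment, patients will undergo a sixminute hall-walk as part of the research substudy. Cardiac output will be assessed noninvasively using the Innocor" inert rebreathing method. The echo sentence then opens "Thereafter, a transthoracic echo (TTE) will be completed as" part of routine care. After that: "Following completion of the echo, LVAD parameters will be recorded and then the pacemaker will be adjusted to the CS-lead ON setting".
- **Interval.** "Then, patients will complete their routine clinic visit, which typically lasts ~60 minutes". This is the only time gap given.
- **Text, CS-ON block.** After the visit, "the patient will repeat the six-minute hall-walk, as well as cardiac output by inert rebreathing technique, and the same echo images will be repeated". The LVAD readings come last.
- **Schedule table.** The first block reads "TTE with Strain Imaging Innocor Cardiac output 6 minute walk test Clinic Visit". The same three tests in the same order follow the visit. The two blocks are labelled RV pacing and CRT pacing. LVAD parameters have no column.

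The stated primary objective is functional capacity, and walk distance heads the list of outcomes. Cardiac output, echo parameters and LVAD parameters are outcomes 2 to 4. All are compared ON v. OFF by paired t-test. Section H promises "hemodynamic parameters (as measured by cardiac output) that result from enabling the CS-lead".

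**The concern.** The two descriptions are different experiments. In the table's order, echo and cardiac output precede any study exercise in their block. In the text's order, cardiac output is the next test after a six-minute walk, at an unstated time, and echo and LVAD readings come later in the same recovery. Staff cannot follow both, and nothing in the section says which governs.

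The stake is the interpretation of outcomes 2 to 4 as acute haemodynamic effects of the pacing setting. Cardiac output soon after a walk depends on how hard the patient walked and how long ago, as well as on the setting. The substudy is looking for a difference in walking between settings, so equal exertion cannot be taken for granted. This is separate from the fixed OFF-then-ON sequence and would remain if the order of the settings were randomised.

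**Working it through.** **Step 1: compare the orders.**

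| Position in block | Text | Schedule table |
|---|---|---|
| 1st | six-minute walk | echo |
| 2nd | cardiac output | cardiac output |
| 3rd | echo | six-minute walk |
| after these | LVAD parameters | not shown |

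Walk and echo change places in both blocks. In the CS-OFF block the text puts the walk first after enrolment and the echo explicitly later. In the CS-ON block the order rests only on the order of listing.

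**Step 2: compare with the main study.** There, the Swan-Ganz measurements are taken at rest before exercise, and the pump speed adjustments are done at rest and finished before the cycle test. The 0.6 L/min in the Power Analysis is a change in resting cardiac output. The substudy table fits that pattern; the text does not.

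**Step 3: effect on the paired contrast.** Let r_ON and r_OFF be the residual exertion in cardiac output when it is measured under each setting. The error in the ON-OFF difference is r_ON − r_OFF.

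- Same order, equal exertion, equal recovery: r_ON = r_OFF and the error is 0.
- Exertion or recovery differing systematically by setting: the error is the difference in residuals, which is bias.
- Recovery time varying haphazardly: the mean error is 0, but the paired differences are noisier.
- Text order in one block and table order in the other: the error is the whole residual of the block measured after the walk.

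**Step 4: illustration only.** The documents give no value for r. Assume that the walk raises cardiac output by 2 L/min and that the excess halves every h = 1 to 2 minutes, so the residual at t minutes is 2 × 2^(−t/h). All results scale with the assumed rise; a rise of 1 L/min would halve them.

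- *Timing.* For h = 1: 0.25 at 3 min and 0.06 at 5 min, a difference of 0.19 L/min. For h = 2: 0.71 and 0.35, a difference of 0.35 L/min. Against 0.6 L/min these are 0.19/0.6 = 31% and 0.35/0.6 = 59%. The substudy section's own acute example, one HFrEF patient, goes from 4.8 to 5.7 L/min, a change of 0.9; against that they are 21% and 39%.
- *Longer walk with CS-ON.* Assume also that a 10% longer walk raises the excess by 10%, or 0.2 L/min. The difference in residuals is 0.2 × 2^(−t/h): 0.025 to 0.07 L/min at 3 min (4% to 12% of 0.6) and 0.006 to 0.035 L/min at 5 min.
- *Later readings.* At 10 min the entire residual is 2 × 2^(−10) = 0.002 to 2 × 2^(−5) = 0.06 L/min.

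The timing figures describe what a two-minute difference does to a reading. If such differences are unsystematic, they widen the spread of the paired differences without shifting the mean. The bias from a longer walk is much smaller on the same model.

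**The case against.** The strongest reply is that a paired comparison protects itself. The text lists the same order under both settings, so a shared residual drops out of the difference. That stands: the text order alone does not produce bias.

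The text is also looser than a strict sequence. The CS-OFF sentence on cardiac output has no time connector, the CS-ON sentence is a list, and silence about rest does not show that there is none. This stands too, which is why carry-over is a possibility and not a finding.

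A reader might infer that the haemodynamic outcomes cannot be separated from the walk. The documents do not support that. Echo and LVAD readings come later in recovery, and under the assumed decay little is left by then. A reader might also take 0.2 to 0.35 L/min as the bias in the ON-OFF difference; it is timing noise under assumed inputs. Nor is the primary objective undermined, since walk distance is not affected by this mechanism.

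Finally, the table may be the newer version: a margin comment about a new figure appears just after it. Whether that comment refers to this table cannot be established, and the text would still need to be brought into line.

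None of this removes the contradiction. Equal exertion and equal recovery are not secured by anything written, and two conflicting orders leave mixed use open.

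**Conclusion.** The contradiction between text and table is certain and needs no assumption. The table reads coherently from left to right, with the clinic visit between the two pacing blocks, so a fault of text extraction is unlikely.

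The consequence is conditional. If the text is followed without adequate rest, cardiac output, and less so echo and LVAD parameters, could be post-exertion values. The ON-OFF difference is then biased or noisier only if exertion or recovery time is unequal, or if the two orders are mixed. The size cannot be computed from the documents. The point bears on outcomes 2 to 4 of the substudy. It should be corrected before the substudy is run, because the correction costs almost nothing and removes an avoidable source of bias and noise.

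**What to change.** Reconcile the text and the table to one order, used identically in both blocks. The table's order is preferable: echo, cardiac output and LVAD parameters at rest, then the walk. Add LVAD parameters to the table, and state the rest condition (posture and minimum quiet time) that applies before these measurements in each block.

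The first walk then falls under RV pacing, as the table already shows, and the clinic visit of about 60 minutes separates it from the second set of resting measurements.

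The cost is one reordered paragraph, one added sentence and a small edit to the table. No procedure or patient is added, and the visit is longer only by any rest period not already taken. The small downside is that the test sequence, and with it the point in the visit at which the setting is changed, moves relative to the present text; the study team should confirm that this is workable in clinic.

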#### D. Description, Risks and Justification of Procedures and Data Collection Tools:

*Right heart catheterization:* risks involve pain/bleeding at site of catheter insertion, infection, pneumothorax, arrhythmias, and chest discomfort. Radiation exposure: there is a very small amount of radiation exposure that will be experienced during insertion of the catheter. The typical amount of radiation exposure is <7mSv. For comparison, the average amount of radiation exposure per year that results from standing outside is around 3-4mSv. These risks will be minimized by applying topical lidocaine cream (numbing medication) and injecting lidocaine over the sight of catheter insertion. All procedures will be performed using sterile technique. Procedures will be performed with use of an ultrasound machine and fluoroscopy – in this manner, all needles, guidewires and catheters will be monitored per standard guidelines and practice patterns. There are no additional risks associated with insertion/removal of a Swan-Ganz catheter prior to insertion of the Millar catheter. Incorporation of the Swan-Ganz catheter will prolong the current study by an estimated 5 minutes.

Arterial line insertion: risks involve pain/bleeding at site of catheter insertion, infection

*Exercise testing*: exercise testing carries a finite risk of adverse cardiovascular events with less than 1/100,000 in healthy individuals, and approximately 1/10,000 in patients with cardiovascular disease. *Arrhythmias during exercise*: during exercise testing, there is a potential for advanced HF patients to develop arrhythmias.

*Fatigue*: during exercise testing, subjects will eventually develop fatigue, as they are encouraged to exercise at submaximal and peak workloads.

Protocol Template CF-146, Effective 7/10/11 Page 8

#### Commented [ 1]: New figure

*Pump speed adjustments:* as the pump speed is increased or decreased, subjects may theoretically feel lightheaded or become short of breath.

Pacemaker setting adjustments (turning the CS-lead ON and OFF): while it is not anticipated that individuals will have any ventricular arrhythmias that result from enabling or disabling the CS-lead of the CRT-D, this is theoretically possible during any adjustment to a pacemaker-defibrillator. This study does not involve adjustment of any "therapies" delivered by the CRT-D, meaning that in the event of an arrhythmia, the CRT-D would provide anti-tachycardia pacing or shocks as necessary by following standard analysis algorithms that are programmed into the device.

*Echo/ultrasound*: there are no significant risks associated with echo or ultrasound. It is possible that patients may feel slight discomfort from a probe sitting over the skin.

Loss of confidentiality: there is a potential risk of loss of confidentiality any time information is collected. Every effort will be made to keep participant information confidential.

*Risks to an embryo, fetus or breast-fed infant:* this is not anticipated, since advanced HF patients are highly discouraged from bearing children, particularly when they are scheduled to undergo CF-LVAD implantation. However, any woman of child-bearing age will undergo a pregnancy test prior to being studied. If a female participant becomes pregnant during they study, she will tell the PI immediately and she will be removed from the study.

## E. Potential Scientific Problems:

1)Recruitment of subjects for testing: The University of Colorado has an active heart failure and LVAD program, with approximately 50 CF-LVADs inserted in 2015 and over 70 patients followed in the advanced heart failure center. There are currently 37 CF-LVAD patients with CRT-D devices that are being followed clinically by the advanced heart failure and electrophysiology programs here at the University of Colorado. Thus, we do not anticipate any difficulty recruiting subjects for this proposal. Healthy volunteers will be recruited by posting flyers around the University of Colorado Anschutz Medical Campus. We will plan to enroll 30 participants with the anticipation that there will be a few dropouts (no more than 5 anticipated).

#### F. Safety Oversight:

The independent Data Safety Monitoring Board (DSMB) that oversees IR study #16-1635 will also oversee all operations of this study, from initiation of the study through completion. The principal investigator ([name]) will regularly report to the DSMB, which will be comprised of the following members (who are not affiliated with the study):

## [name]

Associate Professor of Medicine-Cardiology

Section of Advanced Heart Failure, LVAD and Cardiac Transplant, Division of Cardiology, Department of Medicine

University of Colorado Anschutz Medical Campus [name], MPH

Assistant Professor of Medicine-Cardiology

Section of Advanced Heart Failure, LVAD and Cardiac Transplant, Division of Cardiology, Department of Medicine

University of Colorado Anschutz Medical Campus

Safety Measures: The following safety measures will be in place during the study:

 Consent: the primary investigator ([name]) will carefully review study objectives, procedures involved, and the risks and benefits of the study with the individual being considered for inclusion. Consent will be obtained from a study coordinator only after the individual being considered has had ample time to carefully review the consent form, the coordinator has personally reviewed the consent

Protocol Template CF-146, Effective 7/10/11

form with the individual, and all questions have been answered to the individual's satisfaction. The coordinator will be responsible for finalizing consent (obtaining signatures), but the primary investigator will be available at any time during the consent process to ensure that the individual makes a fully informed decision about whether or not to participate.

- INR goal: Patients with CF-LVADs are managed with blood-thinners (ie, vitamin-K antagonists [coumadin]), with drug dosages adjusted to an INR goal of 2.0-3.0. For the purposes of this study, all blood-thinners prescribed as part of routine care, will be continued. However, recognizing that there are bleeding risks associated with procedures (right heart catheterization) on patients who are anticoagulated, a right heart catheterization will not be performed on individuals who have an INR > 2.5 less than one week prior to the time of procedure. In the event that the INR is > 2.5, the visit will be rescheduled for another time.
- Participant stopping rules:
  - Hemodynamic monitoring: individuals' vital signs will be monitored continuously during all visits of the study. In the event that an individual becomes hemodynamically unstable during exercise, the study will be discontinued. "Hemodynamic instability" includes, but is not limited to: an unexpected reduction in blood pressure; transition from normal to an abnormal rhythm (e.g. sustained ventricular tachycardia or recurrent nonsustained ventricular tachycardia) at any point in time; clinical instability as determined by [name] (an advanced heart failure cardiologist experienced in conducting studies on these types of patients) or any other team member.
  - Patient comfort: an individual being tested may voluntarily withdraw from the study at any point in time, should he/she become uncomfortable or symptomatic (e.g. excessive dyspnea, lightheadedness) at any point in time during exercise. The primary investigator of the study ([name]) recognizes that patient comfort/discomfort may not be reflected by an individual's vital signs – therefore, the study will be discontinued at any point in time at the patient's request, should the individual become symptomatic despite vital signs being normal).
- A member of the cath lab staff will be present at all times during testing, when a test subject has a heart catheter in place. The cath lab staff member will accompany the patient from the cath lab to the CTRC and remain there until testing is completed. This individual will be responsible for monitoring and serve as an "extra set of eyes", to monitor the well-being of the test subject, while the catheter is in place. In addition, [name], the primary investigator for the study, will be present at all times, including the duration of time when a test subject has a catheter in place. To further safety oversight, a CTRC nurse will be present throughout the procedure whether testing is completed in the cath lab or the CTRC.
- The study PI ([name]) recognizes that there inherent risks involved with invasive procedures and exercise testing. Therefore, the PI will have authority to withhold enrollment of any individual into the study if there are concerns about patient safety or comfort, even if that individual meets all other inclusion/exclusion criteria.
- During CRT-D interrogations on visits 1-2, if arrhythmias are detected, this information will be communicated to the patient and to the patient's managing cardiologist.

This study will be registered on clinicaltrials.gov prior to study initiation. This study is similar in design to IRB #16-1635, which is funded in part, through the PI's NIH/NHLBI K23 award. However, this study (IRB #17-1042) is not a written part of the K23 award that was awarded by the NIH/NHLBI. As such, while this study seeks to address similar objectives (ie, to determine limitations in functional capacity of patients with advanced heart failure with CF-LVADs), this is an independent study with its own protocol and consent forms.

